9.3 Procedures

- AEs will be recorded from the time the consent form is signed through 30 days after the last visit (i.e., at the one month follow-up from Visit 7).
 In addition, SAEs will be reported to the appropriate regulatory authorities, the IRB of Record, and investigators in accordance with all applicable laws and regulations.
- AE reporting must also be carried out by each participating site investigator, according to their local policies and procedures, to the IRB responsible for oversight of their subjects. A copy of the IRB's acknowledgement will be forwarded to the study project manager. In addition, all AEs will be recorded on an Adverse Event Log at each site and entered in REDCap within 72 hours of the site staff becoming aware of the event. All AEs must be followed until resolution or stabilization.
- Unanticipated and unexpected problems involving risk to the subject and/or others, whether related or unrelated to participation in the study, must be reported within 24 hours of the site staff becoming aware of the event to the study project manager. The project manager shall report all SAEs to the Sponsor Principal Investigator, who shall review and evaluate the evidence, and collaborate with the site PI on the final determination regarding attribution for reporting purposes to the following: FDA, Data Safety Monitoring Board (DSMB), Advarra, and/ or Cerevel.
- SAEs which occur any time after the study participant has consented until one month (defined as 30 days) after Visit 7 (i.e., at the final followup phone call) which are unexpected and possibly, probably, or definitely related to the research must be reported by the participating site to the study project manager within 24 hours of the site staff becoming aware of the event.
- FDA and Cerevel Reporting
- The Sponsor Principal Investigator's Investigational New Drug (IND) office will report SAEs to the FDA (if required) via an IND Safety Report on 3500A MedWatch form according to FDA 21CFR312.32 within 15 calendar days of the event occurring (within 7 days if the event is fatal or life-threatening). The Sponsor Principal Investigator's project manager will also report to Cerevel within that same time period.
- Advarra Reporting
- Each site investigator and/or designee will promptly report unanticipated problems occurring at the site to Advarra as per their written policies and procedures. SAEs that do not require prompt reporting will be reported at the time of continuing IRB review per their written policies and procedures via the Advarra CIRBI platform.

- Reporting to DSMB and NIMH
- Any actions taken by one entity in response to adverse event reports will be reported to the other entities. SAEs that are unexpected, and possibly, probably, or definitely related to the intervention will be reported to the DSMB by the study project manager in writing within 24 hours of awareness of the event. All other SAEs, expected or nonserious adverse events, will be reported to the DSMB in the DSMB data reports submitted every 6 months or at the time of continuing IRB review of the study, and to the FDA in the IND annual report. DSMB recommendations/outcomes will be made available to the NIMH.
- COVID-19-related AEs and SAEs
- All AEs and SAEs that are confirmed, or suspected to be related to, COVID-19 will be tracked within the REDCap system. These AEs and SAEs will be evaluated and reported using the same criteria as other AEs and SAEs.

9.4 Criteria for stopping study

For individual subjects, the stopping criteria are:

- Withdrawal of consent and/or patient decision;
- Loss to follow up;
- Changes to eligibility based on inclusion/exclusion criteria;
- Clinical judgment of the investigator or at request of subject, sponsor, or regulatory authority;

Criteria for Stopping or Suspending Enrollment:

- •
- Assessment that risks outweigh benefits in the view of either the DSMB, the study investigators or study sponsors
- Decision by sponsors to withdraw funding or cease pursuing completion of the study.

10. STATISTICAL CONSIDERATIONS

10.1 Statistical Design and Power

10.1.1 Primary Endpoint

To test if CVL-562 has dose-related effects in schizophrenia patients on neural biomarkers of D1R/D5R stimulation. The proposed research includes 120 female and male adults (18-45 years) who meet diagnostic criteria for schizophrenia, schizoaffective disorder, or schizophreniform disorder and who are presenting early in their psychosis course (i.e., <5 years of psychosis duration since first frank psychotic episode). We will make every attempt to balance our recruitment

efforts with regard to sex.

All preprocessing of imaging data will follow Human Connectome Project (HCP) pipelines(67). For each CIFTI-based gray-ordinate, least-squares coefficients will be generated independently reflecting BOLD signal during task conditions. We will use a general linear model to fit the hemodynamic response function (HRF) using a finite impulse response function (FIR) for the timepoints covering the encoding (timepoints 1-2) and delay epochs (timepoints 3-14) and the natural decay in the HRF (timepoints 15-20). Assessing the HRF across these 20 timepoints for each task condition (motor, spatial working memory, distractionnear and distraction-far) will allow us to examine the effects of dose response across our epochs of interest. From these general linear models, we will form within-subject contrasts for second-level analyses. We will use non-parametric combination (NPC) to examine the multivariate effects of dose (5 levels) and task condition (motor, spatial working memory, distraction-near and distraction-far) at each timepoint within each voxel of an independently defined mask of spatial working memory regions from the prior work of [name] (co-investigator). When compared with an ANOVA or related MANOVA, NPC provides a more statistically efficient and robust approach for this primary endpoint, while still allowing for testing of dose-dependent effects of drug on the task BOLD signal at different timepoints(68). NPC has the additional advantage of accommodating the multivariate and potentially non-normally distributed nature of our endpoints. Furthermore, NPC maintains better power at fixed sample sizes than traditional multivariate tests, which have increasing power as the number of modalities increases, until an inflection point, after which traditional test power declines. Significant voxels will be determined using non-parametric statistics and corrections for multiple comparisons as appropriate.

As this is a multi-site neuroimaging project, we will validate neuroimaging data acquisition, transfer and processing prior to clinical data collection. These will be tested using members of the research team who will undergo neuroimaging procedures at each site. Scanning the same persons at each site will allow the research team to compare the image acquisition, as well as the collection of behavioral and eye-tracking data, at each site. We have opted for this instead of the exclusive use of phantoms, as task-based images would not be possible to collect with phantoms. Furthermore, we have opted to use research personnel who travel to each site, rather than examining the first few patients recruited, as we would like to examine image acquisition within-subject, and fully compare sites. Use of our recruited patients would not allow for within-subject comparisons of sites as the clinical protocol is meant to be carried out at one site. Ongoing stability of MRI scanners will be checked using regular phantom scanning.

[figure not shown]

Figure 2. Power Calculation for the Primary Endpoint.

Power: The Primary Endpoint is concerned with within-subject repeated measurement of the CVL-562 dose response on the neuroimaging index. Therefore, the key power consideration is for a group-level within-subject t-test for the combined partial t-tests (Cohen's d). With anticipated attrition we anticipate a final sample of N=100 complete patient datasets across all sites. However, given that data quality and retention may lead to smaller eventual samples, we projected detectable effect sizes using a projected power of at least 80%, and p<0.05. Given our study design, and the NPC approach, we will be able to detect small-to-medium effect sizes (0.18-0.37) for sample sizes ranging between 25-100 participants with full data. Here, we provide an illustration of the achieved effect sizes at 80% power across possible sample size ranges (Figure 2).

10.1.2 Secondary Endpoint 1

The dose-response-based change in BOLD signal will be examined for each individual participant to see how many participants exhibit a change in BOLD signal. For each individual, a binary outcome will be calculated based on the dose x timepoint x task condition within subject analysis of BOLD signal. We will report the proportion of participants that exhibits a dose response and assess whether this is related to baseline working memory performance.

10.1.3 Secondary Endpoint 2

We will test if CVL-562 produces a dose-related modulation of sWM performance. We will leverage behavioral data generated during neuroimaging to quantify dose-related CVL-562 effects on sWM performance and also on sWM performance with distraction. Here, the outcome measure will be the sWM performance measured as the angular difference between the target presentation and the participant's response. We will conduct a 4 (task condition--motor, spatial working memory, near-distraction, far-distraction) x 5 (dose) repeated measures ANOVA. Post-hoc analyses will be conducted to demonstrate the directional effects of behavioral performance with respect to dosing. All statistics will be corrected for multiple

comparisons.

10.1.4 Secondary Endpoint 3

We will directly examine the association between sWM performance and task-evoked BOLD signal. An analysis of variance of the dose-dependent effects of CVL-562 on the task-evoked BOLD signal will be conducted as described for the Primary Endpoint, but instead will use the trial-by-trial regressor of sWM performance as a covariate. sWM performance will be measured as described in Secondary Endpoint 2, and will be treated as a covariate of interest in the above-specified general linear model. An effect of a 5 (drug dose) x 4 (task condition) interaction with the sWM precision covariate would indicate that the drug has an effect of BOLD signal change that is specifically associated with a change in trial-by-trial sWM performance.

10.1.5 Secondary Endpoint 4

We will conduct an analysis of variance of the dose-dependent effects of CVL-562 on the functional connectivity of brain regions during spatial working memory. In contrast to the task-evoked modeling, here we will use 'time point' selection methods to isolate specific time points during the delay period of each trial, which we will combine into a time series. This BOLD signal will be used to co-vary a given region of interest with the rest of the brain. Given prior work by our team we will focus on the fronto-parietal control network (FPCN) as a 'seed' region for this task-evoked FC analysis. Specifically, we will quantify covariation of the extracted FPCN signals with all other CIFTI greyordinates. This index of FPCN 'functional integrity' will be obtained across sWM conditions and CVL-562 doses for each subject and will then be entered into 2nd-level random effect analyses.

10.1.6 Secondary Endpoint 5

We will conduct an analysis of variance of the dose-dependent effects of CVL-562 on the resting state functional connectivity using a data-driven global brain connectivity (GBC) metric. Notably, GBC examines connectivity from a given voxel (or area) to all other voxels (or areas) simultaneously by computing average connectivity strength—thereby producing an unbiased approach as to the location of dysconnectivity. Also, unlike typical seed approaches, GBC involves one statistical test per voxel (or area) rather than one test per voxel-to-voxel pairing, substantially reducing multiple comparisons. Per-subject GBC will be obtained for each CIFTI greyordinate at each CVL-562 dose for each subject and will then be entered into 2nd-level random effect analyses.

10.1.7 Secondary Endpoint 6

Resulting resting state GBC maps will be compared against transcriptomic maps of genes relevant to psychotic disease processes from the Allen Human Brain

Atlas (https://human.brain-map.org/) using correlation analyses. This will allow us to see whether spatial patterns of resting state GBC map onto regions enriched for gene expression relevant to schizophrenia and related illnesses.

10.1.8 Exploratory Endpoint 1

We will conduct exploratory analyses to test whether genetic variants are related to BOLD signal changes in response to CVL-562. Genetic variants examined may include, but are not limited to, those genes involved in CVL-562 metabolism, the dopamine 1 receptor, or schizophrenia illness development.

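### Section 10.1.1 gives detectable effects of 0.18-0.37 at p<0.05 for one combined test; the visible text does not show that they hold at the multiplicity-corrected threshold of the primary analysis

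*Combined protocol and SAP*

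**What the plan says.** All of this is in section 10.1.1 of the combined protocol and SAP.

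**Power paragraph.** It says that "the key power consideration is for a group-level within-subject t-test for the combined partial t-tests (Cohen's d". Detectable effects were projected "using a projected power of at least 80%, and p<0.05". The result is that "we will be able to detect small-to-medium effect sizes (0.18-0.37) for sample sizes ranging between 25-100 participants with full data". The paragraph anticipates 100 complete datasets and extends the range downwards "given that data quality and retention may lead to smaller eventual samples". Figure 2 is cited as the illustration; it is not visible in the text available for this review.

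**Analysis paragraph.** NPC is applied to dose (5 levels) and task condition (4 levels) "at each timepoint within each voxel of an independently defined mask of spatial working memory regions". The response is modelled over 20 timepoints: 1-2 for encoding, 3-14 for the delay and 15-20 for the decay ("Assessing the HRF across these 20 timepoints for each task condition"). NPC is preferred partly because it still allows "testing of dose-dependent effects of drug on the task BOLD signal at different timepoints". Inference is described in one sentence: "Significant voxels will be determined using non-parametric statistics and corrections for multiple comparisons as appropriate".

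The visible text gives no correction method, family of tests, mask size, sidedness, or number and correlation of the partial tests.

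**The concern.** The power statement concerns one combined test, and the only error level attached to it is 0.05. The analysis it is meant to support runs many such tests and declares voxels after a correction. A correction normally makes the threshold for each test stricter than 0.05, so an effect detectable with 80% power in one test at 0.05 has less power at the corrected threshold for that same test.

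This matters because 0.18-0.37 is the only sensitivity given for the primary endpoint, and it is offered for samples as small as 25. Section 3 says that the biomarker results are designed to inform subsequent development, and section 2.2.2 speaks of Go/No-Go decisions. Someone who takes the range as the sensitivity of the corrected voxel analysis could read a null map, especially from a reduced sample, as more conclusive than it is.

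**Working it through.** **Inputs from section 10.1.1:** 80% power; 0.05; N=100 paired with d=0.18 and N=25 paired with d=0.37; 20 timepoints. **Assumed, because not stated:** sidedness (both tried) and the size of the corrected family, m.

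**Step 1. Try to reproduce the stated range.** For a single paired contrast with df = N-1, find the noncentrality λ at which the noncentral t gives 80% power. Then d = λ/√N.

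| | N | critical t | λ | d needed | stated d | ratio |
|---|---|---|---|---|---|---|
| two-sided | 100 | 1.984 | 2.829 | 0.283 | 0.18 | 1.57 |
| two-sided | 25 | 2.064 | 2.920 | 0.584 | 0.37 | 1.58 |
| one-sided | 100 | 1.660 | 2.504 | 0.250 | 0.18 | 1.39 |
| one-sided | 25 | 1.711 | 2.560 | 0.512 | 0.37 | 1.38 |

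An uncombined paired test does not reproduce 0.18-0.37. The range relies on a gain of about 1.4 to 1.6 from NPC combination or within-subject correlation. Such a gain is possible: combining about 2.5 independent partial tests would supply it two-sided (1.57² = 2.5), as would a within-subject correlation of about 0.80 if d is on the raw-SD scale (1 - (0.18/0.283)²/2 = 0.80). The text does not give the inputs actually used. The range is therefore unverifiable from the text, not shown to be wrong.

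**Step 2. Grant the gain and change only the threshold.** Keep the λ that gives exactly 80% at two-sided 0.05 (2.829 and 2.920) and test at 0.05/m. The detectable d on the plan's own scale is the stated d × λ(0.05/m)/λ(0.05).

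| m (assumed) | α per test | power, N=100, d=0.18 | detectable d | power, N=25, d=0.37 | detectable d |
|---|---|---|---|---|---|
| 1 | 0.05 | 80% | 0.18 | 80% | 0.37 |
| 5 | 0.01 | 58.2% | 0.221 | 55.7% | 0.466 |
| 20 | 0.0025 | 39.8% | 0.252 | 35.3% | 0.542 |
| 200 | 0.00025 | 17.7% | 0.297 | 12.9% | 0.664 |

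One row in full, for m=20 and N=100: the critical t is 3.103, λ for 80% power is 3.957, and 0.18 × 3.957/2.829 = 0.252. One-sided at m=20, power is 36.2% (N=100) and 32.5% (N=25).

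**Step 3. Replace Bonferroni with a permutation correction, and separate two kinds of power.** Simulate one voxel with 20 timepoints and one combined test per timepoint, set to 80% power at 0.05. Put the effect at all 12 delay timepoints (3-14). Assume AR(1) correlation of 0.5, 0.8 or 0.9 between timepoints, and use a two-sided sign-flip maximum-statistic correction over the 20 timepoints (2,000 trials, 999 permutations, Monte Carlo SE about 1 point or less).

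| | correlation 0.5 | 0.8 | 0.9 |
|---|---|---|---|
| power at a given delay timepoint, N=100 | 40.7% | 45.0% | 48.7% |
| power at a given delay timepoint, N=25 | 36.8% | 41.9% | 46.9% |
| at least one delay timepoint, N=100 | 97.6% | 90.5% | 82.6% |
| at least one delay timepoint, N=25 | 97.2% | 89.5% | 81.7% |

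The answer therefore depends heavily on which power is meant, and the plan does not say. Neither kind includes correction across mask voxels, which cannot be computed without the mask size and method.

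**The case against.** The strongest reply has four parts.

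**The voxel is the declared unit.** Correction is mentioned only in the sentence about voxels, and a family of 20 timepoints is an assumption. Power for at least one timepoint in a voxel stays at or above 80% in Step 3. This stands: the 40% and 35% figures describe one pre-named timepoint and must not be read as the power of the trial. It does not rescue the stated range, because the Step 3 result assumes that all 12 delay timepoints carry the effect and leaves out correction across voxels.

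**Figure 2 may supply what is missing.** It is absent only from the text available here and could state the gain, the threshold or both. This stands and limits the point to what the visible text shows.

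**The 0.05 could already be a corrected level.** The text does not exclude this. A corrected-level calculation would, however, need a family or mask size, or a simulation, and the visible text has none.

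**The power paragraph already says that it concerns a combined t-test.** It does, but it does not say whether 0.05 is adjusted, and the claim of detectability carries no qualification.

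Two stronger readings are tempting and are not supported. A reader might infer from Step 1 that 0.18-0.37 is an arithmetic error; a gain from combination or correlation could produce it. A reader might also infer from the spacing of the endpoints that an unadjusted 0.05 was used. The stated ratio is 0.37/0.18 = 2.06, and rounding allows 1.97 (0.365/0.185) to 2.14 (0.375/0.175). A normal approximation gives √(100/25) = 2.00 at any threshold, and 20 one-sided tests give 2.137, also inside that interval. The spacing cannot tell the two thresholds apart.

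**Conclusion.** The point holds in limited form, with moderate confidence, and should be fixed. On the visible text, 0.18-0.37 is the sensitivity of one combined test at p<0.05; it is not shown to be that of the corrected voxel analysis. If the range refers to an unadjusted two-sided 0.05, power per test falls to between 58% and 18% at N=100, and between 56% and 13% at N=25, over assumed Bonferroni families of 5 to 200. These figures rest on the assumed family, on Bonferroni, and on granting the plan's unexplained gain in full; a permutation correction on correlated data loses somewhat less. The documents do not support the further claim that the trial is underpowered for its primary endpoint, because mask-wide power is unknown.

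**What to change.** In section 10.1.1 and Figure 2, restate the detectable effects for N=25 to 100 at the corrected threshold of the planned NPC analysis, for example from a short simulation of the permutation test. Say whether power is for a given voxel and timepoint or for at least one. Give the correction method, the family (voxels, timepoints or both) and the sidedness. Also give the inputs behind the gain (the scale of d, and the number and correlation of the partial tests), or confirm that Figure 2 gives them.

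If this is not done, and the sponsor confirms it, label 0.18-0.37 as applying to one combined test at an unadjusted 0.05. Do not describe 25 participants as enough to detect small-to-medium effects in the corrected analysis unless the restated calculation supports it.

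The cost is a text edit, or one short simulation plus revised text. Enrolment, conduct and the analysis method do not change. The downside is that the stated sensitivity may become less favourable.

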administration produced 12 hours of clinical improvement (35). It was developed by Pfizer, Inc. and recently acquired by Cerevel Therapeutics, who have agreed to support the proposed trial. As noted above, CVL-562, like all prior pro-cognitive D1R agonists, also stimulates D5R. D5Rs are located on proximal dendrites, while D1Rs are located on dendritic spines and distal dendrites (38). D5R, like D1R, plays an important role in sWM (39). We are taking several steps in this study to address potential implications of the dual actions of CVL-562. First, we are densely mapping the dose-response curve for CVL-562 from marginal occupancy to the limits of tolerability to determine whether there are non-linear (inverted-U) doserelated effects. The moderate intrinsic activity of CVL-562 at D1R may protect against detrimental effects of cognition related to overstimulation of D1R and direct impairment of cognition was not observed in the Pfizer Phase IB SCZ trial. However, it is still possible that this drug produces detrimental effects on cognition (inverted-U dose-response) at given doses due to overstimulation of D5R. Therefore, our study design incorporates a wide range of doses to identify individual responses to each dose and allow us to map individual pharmacologic dose-response profiles.

2.2.4 Ability of responses to single doses to predict the effects of chronic dosing.

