Unfortunately, the initial Phase IB study of CVL-562 in schizophrenia produced negative results and did not provide guidance for dose-selection. Differences between this earlier study and the current study are that we believe that we would optimize patient selection, use more sensitive outcome measures, and map the dose-response relationship more precisely. Prior non-human primate studies, though, describe dose-related improvements in sWM (40), and with chronic intermittent administration, even lower doses of D1R/D5R agonists that were without initial benefit also came to have procognitive effects (32). Thus, we are confident that doses of CVL-562 that produce acute neural signatures of improvement, and secondarily, improvement in sWM would be likely to produce clinical benefits in a subsequent longer clinical trial. As our primary endpoints are imaging in nature, we are also testing to see whether D1 partial agonism affects sWM circuits, with improved sWM performance and the identification of a subset of those who respond to CVL-562 as secondary endpoints. Using these as secondary endpoints could be used in subsequent full-scale clinical trials if our study demonstrates single-dose effects of CVL-562 on associated neural circuits.

2.2.5 Adjusting for antipsychotic effects.

Antipsychotics could complicate this study in three ways: directly competing with dopamine for D1Rs, down-regulating D1Rs and D5Rs (7) and reducing cortical structural connectivity, which might be reflected in antipsychotic-related reductions in cortical volumes (41, 42). To reduce the first risk, we are excluding antipsychotics with high D1R affinity, including olanzapine, clozapine, ziprasidone and asenapine. The second risk is somewhat unavoidable, as D1R/D5R down

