regulation occurs as early as 6 months of antipsychotic treatment (7). Nonetheless, it is essential to determine the benefits of adjunctive CVL-562 in patients engaged in antipsychotic treatment so that findings can generalize to typical treatment settings. However, to minimize the second and third risks, we will limit this study to people early in the course of schizophrenia to limit the cumulative impact of antipsychotic exposure. One additional potential risk is of pharmacokinetic interactions of CVL-562 and antipsychotic medications. CVL-562 is primarily metabolized by the P450 enzyme CYP3A4 (Investigator Brochure). We do not anticipate drug-drug interactions with antipsychotics because neither CVL-562 or the antipsychotics allowed for patients in this project are P450 enzyme inhibitors or inducers (Investigator Brochure). Nonetheless, we will measure plasma CVL-562 levels on each test visit and we will explore whether plasma level is a better predictor than dose of drug effects on our primary and secondary outcome measures. If plasma level is significantly better than dose in predicting biomarker changes, the subsequent clinical trial could target plasma level rather than dose, a strategy that seems to be optimal for some other medications (43).

2.2.6 Optimizing task selection.

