3.1 Primary Endpoint

To test if CVL-562 has dose-related effects in schizophrenia patients on putative neural biomarkers of D1R/D5R stimulation. We will examine the dose-specific effects of CVL-562 on blood oxygen level dependent (BOLD) signal change during working memory procedures. The primary outcome measure is an analysis of variance of the dose-dependent effects of CVL-562 on the blood oxygen level dependent signal (BOLD) during spatial working memory. Post-hoc univariate tests will quantify directional dose-related CVL-562 effects.

3.2 Secondary Endpoint 1

To test in how many participants CVL-562 produces a dose-related modulation of BOLD signal during working memory procedures.

3.3 Secondary Endpoint 2

To test if CVL-562 produces a dose-related modulation of sWM behavioral performance collected during fMRI. This will be examined using the behavioral data generated during neuroimaging to quantify dose-related CVL-562 effects on sWM performance both with and without distractors.

3.4 Secondary Endpoint 3

We plan to directly examine the association between trial-by-trial sWM performance and task-evoked BOLD signal by regressing trial-by-trial sWM performance with and without distractors with the relevant BOLD signal.

3.5 Secondary Endpoint 4

We will examine the dose-dependent effects of CVL-562 on the functional connectivity of brain regions during spatial working memory.

3.6 Secondary Endpoint 5

We will examine the dose-dependent effects of CVL-562 on the resting state functional connectivity using a data-driven global brain connectivity (GBC) metric.

3.7 Secondary Endpoint 6

We will compare the change in resting state GBC as a function of CVL-562 dose with the transcriptomic maps from the Allen Human Brain Atlas relevant to risk genes in schizophrenia.

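### Secondary Endpoint 1 reports a proportion of dose responders from one session per dose per patient, with no responder rule, error term or chance expectation

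*Combined protocol and SAP*

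**What the plan says.** Section 3.2 states the aim at the level of the individual: "To test in how many participants CVL-562 produces a dose-related modulation of BOLD signal during working memory procedures". Section 2.2.3 gives the wider purpose of the dose range: "to identify individual responses to each dose and allow us to map individual pharmacologic dose-response profiles".

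The analysis is in section 10.1.2. It makes one yes/no call per patient: "For each individual, a binary outcome will be calculated based on the dose x timepoint x task condition within subject analysis of BOLD signal". It then says: "We will report the proportion of participants that exhibits a dose response", and relates this to baseline working memory. It gives no per-patient test statistic, error term, cut-off, proportion expected without a drug effect, or interval.

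The nearest method text is the primary analysis in section 10.1.1, which will "examine the multivariate effects of dose (5 levels) and task condition" over 20 timepoints and four conditions. The multiplicity correction mentioned there applies to voxels in that group analysis.

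Section 4.4 assigns placebo, 1, 4, 15 and 25 mg to five visits, with 25 mg on the last visit for 75% of patients. Section 4.2.1 describes four task runs per scan, all after that visit's dose. No level is repeated, and the schedule in section 8 has no pre-dose scan.

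**The concern.** The aim attributes a change in one patient's signal to the drug. With one session per level, a difference between two doses in one patient is also a difference between two days. A per-patient test that measures error only from runs within a session treats every real day-to-day difference as signal. Separately, any test applied to 100 patients gives some positive calls by chance, and the plan sets no number against which to read the count.

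Two results depend on this. Section 2.2.4 says the secondary endpoints, including the identified subset of responders, could be used in later full-scale trials "if our study demonstrates single-dose effects of CVL-562 on associated neural circuits". A proportion with no chance expectation would then carry forward a count that is partly false labels. The planned association with baseline working memory would also use a noisy binary label, which mainly dilutes it.

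**Working it through.** The plan states no figure for this endpoint, so there is none to reproduce.

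**Inputs from the documents.** 100 complete datasets (10.1.1); 5 levels, one session each (4.4); 4 runs per session (4.2.1); 4 conditions and 20 timepoints (10.1.1).

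**Assumptions, not in the documents.** Per-patient alpha 0.05 (10.1.1 uses p<0.05, but only for the primary power statement); all four conditions in every run; noise independent over timepoints; session variance shown as a range.

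**Step 1: chance alone.** With a perfectly calibrated test and no drug effect, the count is Binomial(100, 0.05). The mean is 100 × 0.05 = 5 and the 95% range is 1 to 10. At least 11 labels are needed to exceed chance at one-sided 0.025. This step needs no assumption about session variance.

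**Step 2: aliasing.** With dose as a five-level factor, the dose x timepoint x condition sum of squares depends only on the set of five session profiles, not on which profile carries which dose. Reordering the dose labels in simulated data left F unchanged. A test on within-session error therefore cannot tell dose from session in one patient.

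**Step 3: what cancels.** A session shift common to all conditions and timepoints drops out of the three-way term. So does session-by-condition variation that is constant over timepoints. Only variation in the shape of the condition-specific time course remains.

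**Step 4: illustration.** Take T timepoints and run-level error. Let session-by-condition variance be v times the run variance, following a curve h with mean square 1. Put S = Σ(h − mean h)². With no drug effect, the numerator mean square is

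[(1 + 4vS)·χ²(12) + χ²(12(T − 2))] / (12(T − 1)), with error df 60T.

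For T = 20 and a half-sine sampled at interval midpoints, S = 3.755. The numerator has 12 × 19 = 228 df, the error has 60 × 20 = 1,200 df, and the 5% critical value is 1.177. At v = 0.10, 1 + 4 × 0.10 × 3.755 = 2.50, so the mean numerator is (2.50 × 12 + 216)/228 = 1.08. The chance of exceeding 1.177 is about 20%.

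False labels per 100 patients with no drug effect:

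| Case | v = 0 | 0.05 | 0.10 | 0.20 | 0.30 |
|---|---|---|---|---|---|
| Constant h, T = 20 | 5 | 5 | 5 | 5 | 5 |
| Half-sine, T = 20 | 5 | 11 | 20 | 43 | 63 |
| Gamma-convolved block, T = 20 | 5 | 13 | 25 | 53 | 74 |
| Half-sine, T = 4 | 5 | 7 | 9 | 16 | 23 |
| Dose as mg, T = 20, both curves | 5 | 8–9 | 12–14 | 22–27 | 32–39 |

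Entering dose as a number in mg removes the invariance of step 2, but run-level error still leaves session variation out of the test.

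**Step 5: the association.** Assume 100 patients, a true correlation of 0.5 between response amplitude and baseline working memory, and amplitude with mean 1 to 2 and SD 1 session SD. In simulation a continuous per-patient contrast gave r of about 0.24–0.25 and power 66–72%. A binary label from a calibrated five-session rule gave r of 0.05–0.09 and power 9–14%. Both rejected in 5% when the true correlation was 0. The effect sizes and the form of the contrast are assumed.

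**The case against.** The strongest reply is that step 4 models a test the plan does not name. Section 10.1.1 prefers non-parametric combination to ANOVA for the primary analysis, and 10.1.2 does not say what is used per patient. The table also depends on the assumed curve and on independent noise. A slightly different half-sine grid gives 52 rather than 63 at v = 0.30. With lag-1 correlation 0.8 and a sphericity-corrected F test, the half-sine row becomes about 10, 15, 29 and 45 for v from 0.05 to 0.30. This stands: the table shows a mechanism, not the size of the problem in this trial. Steps 1 to 3 do not depend on it.

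The plan also has partial safeguards. For plasma level, section 2.2.5 says: "we will explore whether plasma level is a better predictor than dose of drug effects on our primary and secondary outcome measures". Dose order is randomised. Caffeine, nicotine, urine THC, in-scan physiology, cerebral blood flow and checkerboard responses are recorded. These could help, but 10.1.2 uses none of them, and randomised order separates visit from dose across patients, not within one patient. Nor does the plan rule out a chance benchmark; it is silent.

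A reader might infer that most labelled responders would be false, or that the proportion could be wholly chance. The documents do not support that. They give no session variance and no test, and 2.2.4 makes later use conditional on drug effects having been shown. If such effects are shown, at least some patients respond.

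**Conclusion.** The point holds in limited form. As written, 10.1.2 yields a count that cannot be read as the number of patients in whom the drug changes the signal. The part free of variance assumptions is the missing benchmark: about 5 of 100 (1 to 10) by chance at an assumed alpha of 0.05. The aliasing of dose with session follows from the design if dose is a five-level factor and the error is within-session. The resulting inflation is unknown and could be nil if session variation is constant over timepoints.

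A reader might also infer that the primary result is undermined. It is not: the primary test is a group-level comparison across patients and does not rest on per-patient labels. For a secondary endpoint that can be repaired in the text, this is a cheap improvement.

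**What to change.** In section 10.1.2:

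1. Prespecify one per-patient statistic on session-level values. It should depend on which session had which dose, be able to detect a non-monotone response, and keep the task conditions of interest, including the distractor conditions. Its form is the sponsor's choice.
2. Report the responder count beside its distribution when dose labels are redrawn under the actual randomisation scheme (the 75/25 placement of 25 mg and the site balance), adjusting for visit. Give the excess over chance and an interval.
3. Use a prespecified continuous per-patient dose contrast, not the binary label, for the association with baseline working memory.
4. Describe individual labels as descriptive, not as a confirmed responder rate.

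No new visits or scans are needed. The cost is some wording, a little more analysis and access to the site-balancing rule, which section 4.4 does not spell out. The count will probably be lower, and few true responders will be labelled. With one candidate statistic (the largest absolute correlation over a linear shape and peaks at 1, 4 and 15 mg), an inverted-U peaking 2 session SDs above placebo is labelled in only about 8–12% of patients, depending on its shape. When all 100 simulated patients responded, 8.3 were labelled against 4.7 under redrawn labels. The excess is therefore evidence that some patients respond, not an estimate of how many.
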